4. A low PEEP strategy was used in both arms of the Papazian trial. For patients with moderate to severe ARDS, meta-analyses suggest that high PEEP strategies may result in improved outcomes including mortality [15]. Based upon the likelihood that atelectrauma may be more common with lower PEEP strategy, neuromuscular blockade may have a different effect for patients receiving a high PEEP strategy.
5. All patients in the control arm of the Papazian trial received heavy sedation defined as a Ramsay score of six. The routine use of heavy sedation is associated with several deleterious outcomes including prolonged length of mechanical ventilation. Based on the results of our survey of PETAL investigators, 86% of respondents reported that the routine sedation goal for ARDS patients is not heavy sedation. Therefore, it is plausible that the positive results of the Papazian trial are related to the harmful and uncommon use of a heavy sedation strategy in the control arm.

6. Safety-related outcomes are commonly underreported in randomized controlled clinical trials resulting in misinterpretation and inadequate conclusions concerning the benefits of the intervention [16, 17]. The assessment of neuromuscular dysfunction was determined using only the MRC score to define weakness. In addition, the potential effects of neuromuscular blockade on the development of symptoms of post-traumatic stress disorder and paralysis recall were not determined. A better understanding of the long term risk associated with the use of neuromuscular blockade would allow clinicians to make a more informed decision about its utility in ARDS.
7. Based on the strength of the previous clinical trials and the need to replicate their results, we propose to test the safety and efficacy of a 48 hour infusion of neuromuscular blockade for reducing mortality in patients with early ARDS. *We hypothesize that early neuromuscular blockade will result in improved clinical outcomes, specifically hospital mortality prior to discharge home before day 90 in patients with moderate-severe ARDS.*

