### 2.3 Analysis Methods for: Secondary Outcomes, Descriptive Variables, Safety Outcomes, Patient Characteristics

Continuous secondary outcomes will be compared between treatment groups using a t-test. Ordinal secondary outcomes (defined as outcomes with ordinal levels such as none, mild, moderate...) will be compared between groups using the Cochran-Mantel-Haenszel ANOVA (row mean score) test. Categorical secondary outcomes will be compared between treatment groups using a Chi-square or Fisher's exact test as appropriate to the sparseness of the data. All tests will use a two sided p=0.05 significance level. There will be no correction for multiple comparison.

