## Appendix:

### Appendix A1: Outcome Variables

Variable	Category	Scale	Method
All-cause mortality prior to discharge home before day 90	Primary Outcome	Binary	Wald-test from 90 day KM estimate
ICU acquired weakness	Secondary Outcome	Binary	Monte Carlo Fisher's Exact Test
IL-6 levels (plasma)	Secondary Outcome	Continuous	T-test
Hospital mortality to day 28	Secondary Outcome	Binary	Chi-square Test
Ventilator free days to day 28	Secondary Outcome	Continuous	T-test
Organ failure free days to day 28	Secondary Outcome	Continuous	T-test
ICU-free days at day 28	Secondary Outcome	Continuous	T-test
Hospital-free days at day 28	Secondary Outcome	Continuous	T-test
Oxygenation Index on study days 1-4,7 PaO 2 / FiO 2 ratio on study days 1-4, 7 Level of PEEP on study days 1-4, 7 Plateau pressure on study day 1-4, 7 Development of pneumothorax through day 7	Physiologic measure	Continuous Continuous Continuous Continuous Binary	T-test T-test T-test T-test Fisher's Exact Test
Disability: using Katz Activities of Daily Living (ADL)/Lawton Instrumental Activities of Daily Living Scale (IADL)	Long term outcome assessments	Binary	Chi-square Test

plus two additional Nagi items			
Health-Related Quality of Life (including utilities): EuroQol (EQ-5D-5L)		Continuous	T-test
Self-rated health: 1 standard item		Continuous	T-test
Pain-interference: 1 standard item		Continuous	T-test
Post-traumatic Stress-like Symptoms: Post-Traumatic Stress Symptoms (PTSS-14)		Binary (Part B Score $\geq 45$ )	Chi-square Test
Cognitive function: Montreal Cognitive Assessment (MoCA-Blind)		Continuous Binary ( $< 26$ )	T-test Chi-square Test
Via proxy, the Alzheimer's Disease 8 (AD8)		Continuous	T-test
Subsequent return to work, hospital and ED use, and location of residence		Categorical	Fisher's Exact Test
Use of rescue procedures	Safety	Binary	Fisher's Exact Test

Paralysis recall, in-hospital	Safety	Binary	Fisher's Exact Test
Supraventricular tachycardia (SVT) or new onset atrial fibrillation	Safety	Binary	Fisher's Exact Test

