#### Post-traumatic Stress-like Symptoms: Post-Traumatic Stress Symptoms (PTSS-14)

Assessed at months 3, 6, and 12 by the subject or the proxy. Part A score was calculated as a sum of all the questions answered as "Yes". The part B score was a sum of all the answers (rated from 1 to 7) with a maximum score ranging from 14 to 98.

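### PTSS-14 is tested only as Part B at or above 45 by chi-square, although the SAP already derives the 14-to-98 score; add the score as a second comparison, as is done for MoCA-Blind.

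*SAP*

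**What the plan says.** The PTSS-14 row of SAP Appendix A1 has one scale, "Binary (Part B Score $\geq 45", and one method, "Chi-square Test". SAP Appendix A3 describes the underlying measure: "The part B score was a sum of all the answers (rated from 1 to 7) with a maximum score ranging from 14 to 98". Neither appendix explains why 45 was chosen or why the cut is the only analysis.

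The next row of A1, MoCA-Blind, is listed as "Continuous Binary ( $< 26" and has both a t-test and a chi-square test.

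SAP 2.3 sets the general rule: "Continuous secondary outcomes will be compared between treatment groups using a t-test". Categorical outcomes get chi-square or Fisher's exact test. It adds: "All tests will use a two sided p=0.05 significance level". There is no multiplicity correction. SAP 2.8 has a rule for continuous and ordinal functional data at follow-up, but it does not name PTSS-14, and A1 classes PTSS-14 as binary.

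Protocol 3.6, item 6, lists among its reservations about the earlier trial that "the potential effects of neuromuscular blockade on the development of symptoms of post-traumatic stress disorder and paralysis recall were not determined".

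**The concern.** The protocol presents stress symptoms after paralysis as a harm question that the earlier trial left open. The plan then collects a graded score and uses only whether it reaches 45. A patient who moves from 20 to 40, or from 50 to 80, contributes nothing to the comparison.

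For a harm question, low power errs in the unsafe direction, because a real general worsening can be reported as no difference. Only survivors who complete an interview contribute, so the information is limited to begin with.

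**Working it through.** **The plan's own figure first.** The documents state no power or sample size for PTSS-14. The only design figure to reproduce is the primary one: 35% v 27%, two-sided 0.05, power 0.90, total 1408. The pooled-variance formula for two proportions, 1:1 (ratio assumed) and without continuity correction, gives 701 per arm, or 1402 in total. Power at 704 per arm is 0.902. This agrees with 1408 to within 3%, so the same formula is used for the chi-square below.

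**Inputs from the documents.** Two-sided 0.05 (SAP 2.3); the Part B range "with a maximum score ranging from 14 to 98" and the cut at 45 (SAP A3 and A1); 704 per arm with planned mortality of 35% and 27% (Protocol section 7).

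**Inputs the documents do not give, assumed here.**
- Response: planned survivors are 704 × 0.65 + 704 × 0.73 = 457.6 + 513.9 = 971.5, about 485 per arm. With 50-100% interviewed this is about 242-485 per arm. The main case is 80%, or 388 per arm.
- Share of controls at or above 45: 10-50%.
- Size of effect: set so that the t-test on the score has 80% or 90% power.
- Shape: normal with a uniform shift first, then skewed scores, then harm in a minority.

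**Step 1, the shift.** The standardized shift for a given t-test power is d = (1.960 + z) × √(2/n). At n = 388 and 80% power, d = (1.960 + 0.842) × √(2/388) = 0.201. At 90% power, d = 0.233.

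**Step 2, cut the same shift at 45.** If p₁ of controls are at or above the cut, the shifted arm has p₂ = 1 − Φ(z₁₋ₚ₁ − d). For p₁ = 0.25, p₂ = 1 − Φ(0.674 − 0.201) = 0.318.

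**Step 3, chi-square power.** Power = Φ{[(p₂ − p₁)√n − 1.960 √(2p̄(1 − p̄))] / √(p₁(1 − p₁) + p₂(1 − p₂))}. With p₁ = 0.25, p₂ = 0.318 and p̄ = 0.284, this is Φ{[1.339 − 1.250] / 0.636} = Φ(0.14) = 0.556. The t-test has 0.80, so the loss is 24 points.

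**Step 4, the full range at 388 per arm.**

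| Controls ≥ 45 | Chi-square power when t-test has 80% | Loss (points) | Chi-square power when t-test has 90% | Loss (points) |
|---|---|---|---|---|
| 10% | 40% | 40 | 51% | 39 |
| 15% | 47% | 33 | 60% | 30 |
| 20% | 52% | 28 | 65% | 25 |
| 25% | 56% | 24 | 68% | 22 |
| 30% | 58% | 22 | 71% | 19 |
| 40% | 60% | 20 | 73% | 17 |
| 50% | 61% | 19 | 73% | 17 |

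Between 242 and 485 per arm the loss changes by about 1 point, so the unknown response rate hardly matters to it. Widening the t-test power to 50-95% gives a loss of 13-40 points.

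**Step 5, other shapes (simulated, with scores rounded and held within 14-98).**
- Skewed scores (14 plus a gamma variable), additive shift, 250 per arm, 15-35% at or above 45, t-test power 80%: the chi-square has 24-54%.
- Skewed scores, proportional effect: the cut loses about 16-20 points.
- Harm only in a minority, t-test power 80%: if the minority moves to scores of 45-65, the chi-square has 88-99%. If it moves to 50-80, the chi-square has 59-91%.

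The direction therefore holds for a general rise in symptoms, but it is not universal.

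**The case against.** Four points can be made for the plan as written.

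*The row follows the SAP's own rule.* A reader might infer that the PTSS-14 row breaches SAP 2.3. The documents do not support that. SAP 2.3 gives t-tests to continuous outcomes and chi-square or Fisher's exact test to categorical ones. A1 declares PTSS-14 binary and assigns chi-square. The issue is the choice of scale.

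*MoCA-Blind is one row among several.* In the same A1 table, the ADL/IADL disability sum (up to 10 points at follow-up) is also treated as binary, and Appendix A2 cuts the ICU Mobility Scale to two levels. Using both forms is not the SAP's general habit. This stands: MoCA-Blind shows that the double listing is available and acceptable to the sponsor, but it does not show that PTSS-14 was an oversight.

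*A rate of high scores is a reasonable target, and can be the more sensitive one.* Protocol 3.6 pairs stress symptoms with paralysis recall, so harm concentrated in a few patients is plausible. Step 5 shows that the cut can then match or beat the t-test. This also stands, and it argues against replacing the cut. It does not argue for the cut alone, because the plan cannot know in advance which form the effect will take.

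*SAP 2.8 may already cover the score.* Its rule for continuous and ordinal follow-up data could be read that way. But it does not name PTSS-14, and A1 classes PTSS-14 as binary. If 2.8 was meant to apply, A1 contradicts it and the same line needs editing.

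**Conclusion.** The concern holds as a conditional loss of information. A derived 14-to-98 score is never compared between arms, no reason is given, and the outcome bears on a harm that the protocol says was left undetermined.

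For a uniform shift in normally distributed scores that a t-test would detect with 80-90% power, the cut costs about 17-28 percentage points if 20-50% of controls score at or above 45, and up to about 40 if 10% do. With skewed scores the cost depends on whether the effect is additive or proportional. If harm falls on a minority pushed above 45, there may be no cost, or a gain.

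A reader might want a single figure for lost power. The documents cannot supply one, because they give no SD, share at or above 45, effect size, effect shape or response rate. A reader might also conclude that the comparison at 45 should become merely supportive. That is a trade-off between two questions, and the minority case shows it could lose power, so it is not recommended here.

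PTSS-14 is one component of one secondary outcome in survivors, with no stated power. Nothing here affects the trial's sample size or its primary analysis.

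**What to change.** In SAP Appendix A1, change the PTSS-14 row to *Continuous; Binary (Part B ≥ 45)* with *T-test; Chi-square Test*, the form already used for MoCA-Blind. At each time point, report the mean difference in Part B with its 95% CI beside the proportion at or above 45 in each arm. Give the two equal standing and report both whatever they show. Add one sentence on why 45 was chosen.

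In the same edit, reconcile the collection rules. Protocol 6.4 has PTSS-14 at 6 and 12 months only and lists it among the measures excepted from proxy response. SAP A3 has it at 3, 6 and 12 months, from the subject or a proxy. This decides which scores enter the test and how many there are.

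The cost is one table row and a sentence; the score is already derived and no new data are needed. The downside is one more uncorrected secondary test per time point. With two tests at 0.05 each, the chance of at least one false positive at a time point is at most 0.05 + 0.05 = 0.10. It will be lower in practice because the two tests use the same scores.

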## Appendix A2: Reference Measurements

Variable	Category	Scale	Method
Time and dose of loading dose		Continuous	Descriptive
Time of initiation of cisatracurium infusion		Continuous	Descriptive
Reason and duration of infusion hold during first 48 hours		Binary>=48.5 hours Continuous	Descriptive
Total dose of cisatracurium infusion during first 96 hours		Continuous	Descriptive
Name and total dose of other NMB during first 96 hours		Dose, Continuous	Descriptive
Additional NMB administered after 96 hours (yes/no)		Binary	Descriptive
Name and total dose of any NMB used in the first 96 hours after randomization (Control Arm)		Binary (Yes/ No) Continuous (Total Dose)	Descriptive
Additional NMB administered after 96 hours (yes/no) (Control Arm)		Binary (Yes/ No) Continuous (Total Dose)	Descriptive

If receiving positive pressure ventilation: Ventilator mode		Categorical, Days 1-4 & 7	Monte Carlo Fisher's Exact Test
If receiving positive pressure ventilation: set rate actual rate minute ventilation tidal volume FiO 2 PEEP I:E ratio, plateau, peak, mean airway pressures set peak flow, set inspiratory time		Continuous, Days 1-4 & 7	T-Test
PaO 2 , PaCO 2 , pH, and SpO 2		Continuous, Days 1-4 & 7	T-Test
Serum electrolytes and glucose		Continuous, Days 1-4 & 7	T-Test
Intravenous sedatives Intravenous opioids Enteral or intravenous corticosteroids		Binary, Days 1-4 & 7	Chi-Square Test
Sedation score: If RASS < -1 (or Riker < 3, Ramsay > 3), and sedation given, list reason given		Reasons (Categorical) Scale Used (Categorical) Light/ Deep/ Agitation (Categorical) Mean score (Continuous)	Chi-square Test Chi-square Test Chi-square Test T-test
Was a sedation interruption performed? Y/N		Binary Daily	Chi-square Test

Fluid intake and output/CVP if available		Continuous	T-Test
ICU Mobility Scale	Safety	Binary (Able to sit at edge of bed or greater)	Fisher's Exact Test
Manual Muscle Testing	Safety	Continuous	T-test

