### 3.9.2 SECONDARY OUTCOMES

#### 1. ICU acquired weakness

- a. Manual muscle strength testing will be attempted at study day 7, and then every 7 days thereafter, until hospital discharge or day 28 (whichever comes first). Patients will be defined as having ICU acquired weakness if their Medical Research Council (MRC) score is < 48 (or mean MRC < 4 for each muscle group tested)[18, 19].
- b. Highest level of mobility will be assessed on study days 1-7 using the ICU Mobility Scale [20], and then every 7 days thereafter, until hospital discharge or day 28 (whichever comes first).

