#### Reference Measurements (Daily)

The following parameters will be measured and recorded between 4:00 and 10:00 A.M. using the values closest to 8:00 A.M. on the days specified in the Time-Events schedule. The following conditions will be ensured prior to measurements: no endobronchial suctioning for 10 minutes; no invasive procedures or ventilator changes for 30 minutes. All vascular pressures will be zero-referenced to the mid-axillary line.

1. If receiving positive pressure ventilation: Ventilator mode, set rate, actual rate, minute ventilation, tidal volume, FiO2, PEEP, I:E ratio, plateau, peak, mean airway pressures, set peak flow, and set inspiratory time
2. PaO2, PaCO2, pH, and SpO2

Values for the following variables will be recorded for the dates shown in the Time-Events Schedule. If the measurements are not obtained during the 6-hour reference interval (4:00 to 10:00 A.M.), then the value obtained closest in time to the reference interval on the respective date will be recorded. If more than one value is obtained during the reference interval, then the value obtained closest to 8:00 A.M. will be recorded.

3. Rescue procedures used
  - a) Proning
  - b) Inhaled nitric oxide
  - c) Epoprostenol sodium
  - d) High frequency ventilation

- e) ECMO
- 4. Serum electrolytes and glucose
- 5. Administration of the following medication infusions:
  - a) Intravenous sedatives
  - b) Intravenous opioids
  - c) Enteral or intravenous corticosteroids ( $\geq$  20 methylprednisolone equivalents)
- 6. Sedation score: If RASS  $<$  -1 (or Riker  $<$  3, Ramsay  $>$  3), and sedation given, list reason given
- 7. Was a sedation interruption performed? Y/N
- 8. Modified SOFA
- 9. Fluid intake and output/CVP if available
- 10. ICU Mobility Scale: Score 0-10 (see Appendix M)

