## L ICU MOBILITY SCALE [20]

	Classification	Definition
0	Nothing (lying in bed)	Passively rolled or passively exercised by staff, but not actively moving
1	Sitting in bed, exercising in bed	Any activity in bed including rolling, bridging, active exercises, cycle ergometry and active assisted exercises; not moving out of bed or over edge of bed
2	Passively moving to chair (no standing)	Hoist, passive lift or slide transfer, to the chair, with no standing or sitting on the edge of the bed
3	Sitting over edge of bed	May be assisted by staff, but involves actively sitting over the edge of the bed with some trunk control
4	Standing	Weight bearing through the feet in the standing position, with or without assistance. This may include use of a standing lifter device or tilt table.
5	Transferring bed to chair	Able to step or shuffle through standing to the chair. This involves actively transferring the weight from one leg to the other to move to the chair. If the patient has been stood with the assistance of a medical device, they must step to the chair (not included if the patient is wheeled in a standing lifter device).
6	Marching on spot (at bedside)	Able to walk on the spot by lifting alternate feet (must be able to step at least 4 times, twice on each foot), with or without assistance.
7	Walking with assistance of 2 or more people	Walking away from bed/chair by at least 5 m (5 yards) assisted by 2 or more people
8	Walking with assistance of 1 person	Walking away from bed/chair by at least 5 m (5 yards) assisted by 1 person
9	Walking independently with a gait aid	Walking away from bed/chair by at least 5 m (5 yards) with a gait aid but no assistance from another person. In a wheelchair bound person, this activity involves wheeling the chair 5m (5 yards) away from the bed/chair.
10	Walking independently without a gait aid	Walking away from bed/chair by at least 5 m (5 yards) without a gait aid, or assistance from another person.

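### The 0-10 ICU Mobility Scale is tested only as able or unable to sit at the edge of the bed, with no reason given and no full-scale analysis

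*SAP*

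**What the plan says.** **Collection.** Protocol 3.9.2, item 1b under the secondary outcome ICU acquired weakness, says "Highest level of mobility will be assessed on study days 1-7 using the ICU Mobility Scale", then every 7 days until hospital discharge or day 28. The daily reference measurements in Protocol 6.3.2 list "ICU Mobility Scale: Score 0-10 (see Appendix M"). The protocol's appendix on the scale defines 11 ordered levels, from lying in bed (0) to walking without an aid (10). Level 3 is "Sitting over edge of bed".

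**Analysis.** SAP Appendix A2 gives the scale one row: category Safety, scale "Binary (Able to sit at edge of bed or greater"), method Fisher's exact test. The row names no day; SAP 2.4 has daily variables compared on each day measured.

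**General rule.** SAP 2.3, whose heading covers secondary and safety outcomes, says that ordinal secondary outcomes "will be compared between groups using the Cochran-Mantel-Haenszel ANOVA (row mean score) test". Categorical secondary outcomes are compared "using a Chi-square or Fisher's exact test as appropriate to the sparseness of the data". Tests are two-sided at 0.05 without correction for multiple comparisons.

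**The concern.** Cutting at level 3 puts a patient who walks unaided (10) in the same class as one who sits over the bed edge (3). It also puts one who is hoisted to a chair (2) with one who only lies in bed (0). No other row of the SAP analyses the full score, and no reason is given for the cut.

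Mobility matters in this trial. Protocol 3.1 names inadequate assessment of muscle paresis as a limitation of the French trial that is being re-tested. Protocol 3.6 adds that neuromuscular dysfunction was judged there by the MRC score alone. The mobility scale is the in-hospital measure under the first secondary outcome that goes beyond the MRC score. If blockade and deep sedation delay standing or walking, the planned test may not show it.

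**Working it through.** **1. Two kinds of change that the cut cannot see.** Fisher's test uses only the count at level 3 or above in each arm. If treatment moves patients from walking (7 to 10) to standing or sitting (3 to 4), that count does not change, and the rejection rate stays at or below 5%. The same holds for moves among levels 0 to 2. This needs no assumption about the data.

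**2. What the documents supply.** Alpha is 0.05 two-sided and the maximum N is 1408, or 704 per arm if allocation is 1:1 (the ratio is not stated). No power is stated for mobility, and no distribution, effect or number assessed is given. The only stated power is for mortality, which serves to check the formula used below:

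power = Φ[(p₁ − p₂ − 1.96·s₀)/s₁], with s₀ = √(2p̄(1−p̄)/n) and s₁ = √((p₁(1−p₁)+p₂(1−p₂))/n).

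For 35% v 27% and n = 704: s₀ = 0.02465, s₁ = 0.02456, and power = Φ[(0.08 − 0.0483)/0.02456] = Φ(1.29) = 0.90, as the protocol states.

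**3. An example that can be followed by hand.** Assume that all 11 levels are equally likely in controls, a common odds ratio of 1.35 towards lower mobility, and 400 assessed per arm.

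- Cut at level 3: control 8/11 = 0.727, odds 2.667. Treated odds 2.667/1.35 = 1.975, so 0.664. Difference 0.0634, s₀ = 0.0325, s₁ = 0.0325. Power ≈ Φ(−0.01) ≈ 0.50 for an uncorrected chi-square test. Fisher's test is conservative; simulation (4000 trials) gives 46%.
- Full score: P(score ≥ k) is (11−k)/11 in controls and (11−k)/((11−k)+1.35k) in the treated. Summed over k = 1 to 10, the means are 5.00 and 4.46, with variances 10.00 and 9.88. SE = √(19.88/400) = 0.223, z = 0.544/0.223 = 2.44, power ≈ Φ(0.48) = 0.68. Simulation of the row mean score test gives 67%.

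The gain is 67 − 46 = 21 points. About 4 of these (50 − 46) come from Fisher's conservatism rather than from the cut.

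**4. Simulated power with 450 per arm** (common odds ratio; the spread over levels is assumed):

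| Assumed share at level 3 or above | Odds ratio | Fisher on the cut | Row mean score, 0-10 | Gain (points) |
|---|---|---|---|---|
| 15% | 1.3 | 24% | 38% | 14 |
| 15% | 1.5 | 48% | 71% | 23 |
| 28% | 1.3 | 37% | 48% | 11 |
| 28% | 1.5 | 70% | 83% | 13 |
| 50% | 1.3 | 45% | 57% | 12 |
| 50% | 1.5 | 84% | 92% | 8 |

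A second set of assumed distributions, also with 450 per arm, gave about 8 to 26 points.

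**5. Wider assumptions.** With 200, 400 or 704 per arm, odds ratios 1.25 to 1.5, six distributions with 8% to 89% at or above the cut, and integer or rank scores, the gain was 3 to 50 points. For distributions with 27% to 77% at or above the cut it was 3 to 26.

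**6. When the effect is not a common odds ratio** (400 or 704 per arm):

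| Pattern | Fisher on the cut | Row mean score |
|---|---|---|
| 5% to 9% of patients move from level 3 to level 2 only | 28-93% | 6-9% |
| 5% or 10% move from walking to sitting or standing | 4-5% | 20-87% |

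Which test does better therefore depends on where on the scale the effect falls.

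**The case against.** **The SAP does not plainly break its own rule.** A reader might infer a breach of SAP 2.3. The row mean score sentence speaks of ordinal secondary outcomes. Appendix A2 labels the scale Safety and Binary, and the list in SAP 1.5 does not name mobility. Once declared binary, the variable fits the chi-square or Fisher rule. Appendix A, which is meant to fix each variable's method, assigns the row mean score test to no variable. This stands as far as it goes. But the heading of 2.3 includes safety outcomes and the protocol puts mobility under a secondary outcome, so the places are unreconciled.

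**The loss of power is not a fact about this trial.** A reader might take a fixed loss from the table above. Every input beyond alpha is assumed, a common odds ratio favours the full-scale test by construction, and the result reverses for an effect at the level 3 to 2 step. This stands.

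**Strength keeps a full-range test.** A reader might infer that weakness goes without one. In fact A2 analyses Manual Muscle Testing as continuous by t-test, and Appendix A1 tests ICU acquired weakness. This limits what is at stake, but does not replace the mobility score. Muscle testing starts on day 7 and requires the patient to pass awakening and comprehension commands; mobility is scored from day 1, and Protocol 6.3.2 does not apply those commands to it.

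**The cut is an interpretable milestone.** Level 3 is the first level that involves actively sitting over the bed edge. That is a good reason to report the proportion, but the SAP does not give it, and it does not require dropping the rest of the scale. Elsewhere the SAP keeps both forms: MoCA-Blind is continuous and binary, and the sedation score is categorical and a mean.

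**Conclusion.** The point holds as an unexplained and unreconciled analysis choice. An 11-level score collected under a secondary outcome is reduced to one cut, and the SAP's own method for ordered data is not used. That changes wholly above or below level 3 are invisible to the planned test follows from the text alone.

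The size is conditional: roughly 8 to 26 points of power with 450 assessed per arm and a common odds ratio of 1.3 to 1.5, and 3 to 50 points across wider assumptions. The sign reverses if the effect lies only at the edge-of-bed boundary. The documents do not support reading this as a breach of SAP 2.3, as a known loss of power, or as leaving weakness without a full-range test. The primary outcome is not affected. It is a cheap improvement.

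**What to change.** In the ICU Mobility Scale row of SAP Appendix A2, enter the scale as ordinal (0-10) and the method as the row mean score test, on each assessment day (days 1-7, 14, 21 and 28). Keep the proportion able to sit at the edge of the bed or better as a supportive summary, with the difference between arms and its confidence interval. If the sponsor prefers the cut as the test, the SAP should say why and reconcile A2 with SAP 2.3 and Protocol 3.9.2.

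The cost is one table row; no new data are needed and no clinical procedure changes. The downside is that a difference in mean score is less simple to describe than a milestone, and that there is less power for an effect confined to the level 3 to 2 step. Keeping the edge-of-bed difference with its interval leaves such an effect visible.
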